A Pediatric Trial Using Tranexamic Acid in Thrombocytopenia

A Prospective Single-Center, Double-Blinded, Randomized Study to Evaluate the Feasibility of using Tranexamic Acid to Reduce Bleeding Complications in Pediatric Patients with Hypoproliferative Thrombocytopenia.

Version 3.0

Version Date: 12 January 2020

NCT03806556

Protocol Synopsis

Patients receiving chemotherapy are at high risk of bleeding complications during the course of therapy, due to a variety of contributing factors. These include, but are not limited to the effects of thrombocytopenia, platelet dysfunction, vascular defects, coagulopathy and the adverse effects of medications received during the course of therapy [1]. Prior reviews on the subject have concluded that major bleeding episodes are associated with increased mortality rates, greater utilization of resources and an increased transfusion requirement [2]. Risks may be even greater in the pediatric population. The Determination of the Optimal Platelet Dose Strategy to Prevent Bleeding in Thrombocytopenic Patients (PLADO) trial enrolled 200 pediatric patients, and found that the population of pediatric patients under study had a greater risk of bleeding events when compared to the adult patients. Bleeding occurred in up to 88% of pediatric patients despite the use of a prophylactic platelet transfusion threshold of $\leq 10,000/\mu\text{L}$ [3].

The appropriate strategy to address this risk is unclear. Prophylactic platelet transfusions are associated with a reduction in clinically significant bleeding compared to a therapeutic transfusion strategy [4]. However, trials evaluating the effectiveness of higher platelet transfusion thresholds have not demonstrated a commensurate decrease in bleeding incidence or severity [5-7]. Other strategies have included the use of higher dose platelet transfusions, which have also been found to be ineffective [8]. Therefore, alternative strategies to prevent bleeding events in thrombocytopenic patients must be identified to reduce the morbidity, mortality and increased transfusion requirements associated with such events.

Tranexamic Acid is a competitive inhibitor of plasminogen activation and inhibits fibrinolysis. It is available in an intravenous formulation and has been used in pediatric patients to prevent or reduce bleeding in the peri-operative setting, pediatric trauma and with menstrual bleeding [9-14]. Prior studies investigating the use of antifibrinolytic agents in patients with hypoproliferative thrombocytopenia have been limited, but results are encouraging as to its effectiveness [15-18]. However, none of these studies have included pediatric patients to date.

The results of this study will allow the investigators to evaluate recruitment success in order to plan for a larger trial to investigate the efficacy of tranexamic acid in this population. It will also provide evidence as to the safety of tranexamic acid when used as an adjunct to platelet transfusion in pediatric patients with hypoproliferative thrombocytopenia, and may provide a signal as to its effectiveness. Lastly laboratory studies will demonstrate whether the dose strategy for TXA effectively suppresses *in vitro* measures of fibrinolysis. If beneficial, this treatment could potentially lead to a decrease in bleeding episodes and platelet transfusions (with an attendant decrease in transfusion related adverse events) as well as potential savings for healthcare-related costs and improved quality of life.

Objectives

The purpose of this study is to evaluate the feasibility and safety of a randomized controlled trial of tranexamic acid for use in the prevention of bleeding complications in pediatric patients with hypoproliferative thrombocytopenia secondary to chemotherapy or blood and marrow transplantation. A secondary objective is to demonstrate that the TXA dosing strategy suppresses in-vitro measures of fibrinolysis.

Study Design

This will be a double blind, randomized, placebo-controlled trial. Eligible subjects will be identified by research staff or primary physicians after being identified as likely to have platelet counts of $\leq 20,000/\mu\text{L}$ for 5 days or longer. Daily assessments of hemostasis and thrombosis will be conducted via chart review, patient interviews and physical exams.

Table of Contents

1. Summary	7
Figure 1: Trial Entry, Randomization, Treatment and Monitoring Flow Diagram	12
2. Background	13
3. Study Aims and Endpoints	14
3.1: Primary Aims and Endpoints	14
3.2: Secondary Aims and Endpoints	14
3.3: Safety Endpoints	15
4. Population	15

Source(s) of monetary or material support	Internal
Contact for public queries	
[name], MD, [[contact]] [[contact]]
 
[name], MD [[contact]]

Contact for scientific queries	
[name], MD The Children's Hospital of Pittsburgh of UPMC Pittsburgh, PA, USA

Public title	A Pediatric Trial Using Tranexamic Acid in Thrombocytopenia
Scientific title	A Prospective, Single-Center, Double-Blinded, Randomized Study to Evaluate the Feasibility of using Tranexamic Acid to Reduce Bleeding Complications in Pediatric Patients with Hypoproliferative Thrombocytopenia
Countries of recruitment	USA
Health condition(s) or problem(s) studied	Thrombocytopenia, Malignancy

Data category	Information
Intervention(s)	
Active comparator: Tranexamic Acid 10 mg/kg IV q8H (or TID if preferred by primary physician) Placebo comparator: Normal Saline IV q8H (or TID if preferred by primary physician)

Key inclusion and exclusion criteria	
Ages eligible for study: ≥ 2 years, ≤ 21 years Sexes eligible for study: both Accepts healthy volunteers: no
 
Inclusion criteria (all must be present):
 
 • Patient hospitalized • Confirmed diagnosis of hematologic malignancy or solid tumor • Undergoing or planned chemotherapy or blood or marrow transplantation • Expected period of thrombocytopenia resulting in platelet count of $\leq 20,000/uL$ for ≥ 5 days • Requires platelet transfusion threshold $\leq 30,000/uL$ • >14 days beyond last dose of PEG-Asparaginase or >72 hours beyond last dose of Erwinia Asparaginase 
Exclusion criteria (none must be present):
 
 • Diagnosis of acute promyelocytic leukemia • History of ITP, TTP or HUS • Known inherited or acquired bleeding disorder

Data category	Information
	
 • Known inherited or acquired prothrombotic disorder • Diagnosis of DIC • WHO Grade 2 or greater bleeding within 48 hours prior to enrollment or study drug activation • Receipt of PEG-asparaginase within 7 days prior to enrollment • Receiving tranexamic acid (or other anti-fibrinolytic agent) or any other pro-coagulant agent; Receiving estrogen derivatives or progestins • Receiving therapy with anticoagulation or antiplatelet therapy • Receiving platelet growth factors • History of thromboembolic event within past six months • History of sinusoidal obstruction syndrome • Visible hematuria • Renal dysfunction (as defined in Section 6, Table 2), receiving dialysis or anuria (defined as <10mL/hr urine over 24H) • History of seizures • Known allergy to tranexamic acid • Pregnancy • Receiving outpatient therapy or predicted to have inpatient hospital stay ≤3 days • Patient with platelet count ≥30,000/uL without predicted fall in platelet count
Study type	
Interventional Allocation: randomized, 1:1 Intervention model: parallel assignment Masking: double blind (subject,

Data category	Information
	
caregiver, investigator, outcomes assessor) Primary purpose: Prevention Phase I
 
Study Period: 18 months

Date of first enrollment	TBD
Target sample size	20
Recruitment status	Pre-Recruitment
Primary outcome(s)	
Determine the feasibility of enrolling and conducting an RCT of tranexamic acid in pediatric patients with hypoproliferative thrombocytopenia
 
To define and describe safety of tranexamic acid administered on this schedule
 
To demonstrate appropriate suppression of in vitro fibrinolytic activity by tranexamic acid administered on this schedule

Key secondary outcomes	
To preliminarily define the reduction in WHO grade 2 or higher bleeding events within the confines of a Phase 1 study
 
To assess the reduction in number of platelet transfusions
 
To assess the reduction in number of red blood cell transfusions

Figure 1. Study Schematic

2. Background

Patients receiving chemotherapy are at high risk of bleeding complications during the course of therapy, due to a variety of contributing factors. These include, but are not limited to the effects of thrombocytopenia, platelet dysfunction, vascular defects, coagulopathy and the adverse effects of medications received during the course of therapy [1]. Prior reviews on the subject have concluded that major bleeding episodes are associated with increased mortality rates, greater utilization of resources and an increase in transfusion requirements [2]. Risks may be even greater in the pediatric population. The Determination of the Optimal Platelet Dose Strategy to Prevent Bleeding in Thrombocytopenic Patients (PLADO) trial enrolled 200 pediatric patients, and found that the population of pediatric patients under study had a greater risk of bleeding events when compared to adult patients. Bleeding occurred in up to 88% of pediatric patients despite the use of a prophylactic platelet transfusion threshold of $\leq 10,000/\mu\text{L}$ [3].

The appropriate strategy to address this risk is unclear. Prophylactic platelet transfusions have been shown to lead to a reduction in clinically significant bleeding compared to a therapeutic transfusion strategy [4]. However, trials evaluating the effectiveness of using a high platelet transfusion threshold have not demonstrated a commensurate decrease in bleeding incidence or severity [5-7]. Other strategies have included the use of higher dose platelet transfusions, which have also been found to be ineffective in reducing the incidence of bleeding [8]. A single-institution study of blood product transfusion requirements in a pediatric hematology/oncology population found that 66% of patients received transfusion of red blood cell or platelet products during the study period [19]. The burden associated with blood product transfusions includes the risk of adverse effects associated with transfusion, affecting up to 10% of transfusions [20]. Multiple platelet transfusions can also be associated with significant costs, in 2018 Medicaid set reimbursement for a unit of irradiated, leukoreduced red blood cells at \$167.64. Therefore, alternative strategies to prevent bleeding events in thrombocytopenic patients must be identified to reduce the morbidity, mortality and increased transfusion requirements associated with such events.

Anti-fibrinolytic agents, including Tranexamic Acid and Aminocaproic Acid, are competitive inhibitors of plasminogen activation and inhibit fibrinolysis. Tranexamic acid is available in an intravenous formulation and has been used in pediatric patients to prevent or reduce bleeding in the peri-operative setting, cases of trauma and with menstrual bleeding [9-14]. Prior studies investigating the use of antifibrinolytic agents in patients with hypoproliferative thrombocytopenia have been limited, but results are encouraging as to its effectiveness [15-18]. However, many of these studies have been small and did not include pediatric patients. At this time there are multiple large randomized controlled trials underway investigating whether antifibrinolytic agents can mitigate the incidence of bleeding and transfusion in patients with malignancies receiving chemotherapy. However, these are limited to adult participants. Given that the rate of bleeding events is even greater in the pediatric population, it stands to reason that antifibrinolytics may be beneficial in this population as well.

The dose of tranexamic acid chosen for this study, 10mg/kg q8H or TID, was chosen from the package insert for Tranexamic Acid, and has been safely used in pediatric patients for other indications. One of the major concerns regarding the use of antifibrinolytics is their theoretical risk of thromboembolic events. Tranexamic acid has been used widely in several major studies, including the CRASH-2 trial and the WOMAN trial, neither of which showed evidence for an increased risk of thromboembolic event in participants receiving tranexamic acid versus placebo [21, 22]. In order to provide an additional layer of caution we will also plan to exclude all patients with a current or past history of thromboembolic disease, current bleeding or coagulation disorders.

Additionally, this study will incorporate a secondary translational component utilizing assays of fibrinolysis on samples obtained from patients prior to and following antifibrinolytic therapy. As this study will not be adequately powered to detect differences in the occurrence of bleeding events between patients in the treatment group and the placebo group, identification of the successful impairment of fibrinolysis *in vitro* will provide evidence of adequate antifibrinolytic dosing. Additionally, by better characterizing baseline fibrinolytic activity in pediatric patients with malignancies, this may allow us to identify a subset of patients in whom antifibrinolytic therapy may be the most useful.

3. Study Aims and Endpoints

3.1 Primary Aims and Endpoints

Aim 1: To determine the safety and feasibility of the use of tranexamic acid in pediatric patients receiving chemotherapy or blood and/or marrow transplantation (BMT)

Endpoint: Incidence of adverse events, serious adverse events and death attributed to study drug; Number of patients screened eligible for enrollment and the rate of recruitment during study period

Aim 2: To evaluate the effectiveness of current dose of tranexamic acid for suppressing *in vitro* fibrinolysis

Endpoint: Measures of fibrinolytic activity at baseline (prior to tranexamic acid infusion) and at steady-state

3.2 Secondary Aims and Endpoints

Aim 3: To determine whether tranexamic acid leads to a decrease in the incidence of WHO Grade 2 or higher bleeding events

Endpoint: Proportion of patients with WHO Grade 2 or higher bleeding events daily following activation of study drug or placebo

Aim 4: To determine whether tranexamic acid leads to a reduction in the number of days with any grade bleeding event

Endpoint: Proportion of patients with any grade bleeding event following activation of study drug

Aim 5: To determine whether tranexamic acid leads to a decrease in the highest observed grade of bleeding (as measured on WHO bleeding scale) during the study period

Endpoint: Highest grade of bleeding (as measured on WHO bleeding scale) during study period in each enrolled patient

Aim 6: To determine whether tranexamic acid leads to a reduction in the number of red blood cell or platelet transfusions required

Endpoint: Number of red blood cell or platelet transfusions per patient daily following activation of study drug

Aim 7: To determine whether tranexamic acid prolongs the amount of time from activation of study drug to the first episode of WHO Grade 2 or higher bleeding

Endpoint: Length of time from activation of study drug to first episode of WHO Grade 2 or higher bleeding

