8.5 Days 2-30 of Study Drug

- Hemostatic/Bleeding Assessment
- Thrombotic Assessment (via chart review)
- Laboratory Assessment
 - CBC – to be drawn daily
 - Serum Creatinine – to be drawn daily
 - Bilirubin level – to be drawn once weekly
 - Fibrinolysis labs – to be drawn on Day 5 (+/- 1 day)
- Data on Platelet Transfusions
 - Number of platelets transfused
 - Source of platelet transfusions (apheresis or whole blood)
 - HLA or cross-match compatible
 - Reason for transfusion
- Data on Red Blood Cell Transfusions
 - Number of units transfused
 - Reason for transfusion
- Adverse Event Assessment and Reporting - All Grade 3 or greater adverse events will be documented and followed
- Medication Review – Document new or discontinued medications

8.6 Day 7 (+/- 3 days) and Day 30 (+/- 3 days) following Discontinuation of Study Drug

- Hemostatic/Bleeding Assessment (via phone conversation or clinic visit for patients who have been discharged; via chart review for patients who remain inpatient)
- Thrombotic Assessment (via phone conversation or clinic visit for patients who have been discharged; via chart review for patients who remain inpatient)

- Adverse Event Assessment and Reporting (via phone conversation or clinic visit for patients who have been discharged; via chart review for patients who remain inpatient). All Grade 3 or greater adverse events will be documented and followed

Table 3. Timeline for Study Assessment

Schedule of Events	Pre-Treatment Period					Treatment Period		Post-Treatment Period
	Pre-Screening	Day of Enrollment ₁	Days Between Enrollment and Randomization	Day of Randomization ₁	Days Between Randomization and Activation	Day 1 of Study Drug	Days 2-30 of Study Drug	
Event								Day 7 (+/- 3 days) and Day 30 (+/- 3 days) after Discontinuation of Study Drug
Medical Chart Review	X							
Informed Consent		X						
Demographics and Medical History		X						
ABO Type		X						
HLA Testing*		X						
Fibrinolysis Labs						X	X ₂	
CBC		X	X	X	X	X	X	
Serum Creatinine		X		X		X	X	
Urinalysis				X ₃		X ₃		
Coagulation Profile (PT/PTT/INR /Fibrinogen/ D-dimer)		X ₄		X				

Pregnancy Test		X ₅		X ₅				
Bilirubin level							X ₆	
Bleeding Assessment				X		X	X	X
Thrombotic Assessment		X	X ₇	X	X ₇	X	X	X
Data on Transfusion				X		X	X	
Drug or Placebo Administered						X	X	
Adverse Event Assessment						ongoing		
Medication Review	ongoing							

1. Lab studies obtained within 24H period prior to enrollment or randomization do not need to be repeated

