11.1.2 Secondary Endpoints

- Assessment of the effect of tranexamic acid on bleeding will consider the difference in the proportion of patients experiencing WHO Grade 2 or higher bleeding between the two study arms following activation of the study drug and until study drug cessation, the proportion of patients with any grade bleeding event following activation of study drug, the highest grade of bleeding experienced during study period and the length of time from study drug activation to WHO Grade 2 or higher bleeding event
- Assessment of the effect of tranexamic acid on platelet transfusion requirement will consider the difference in the number of platelet transfusions administered per patient between the study arms following activation of the study drug and until study drug cessation.

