11.3 Analysis Populations

Participants will be analyzed according to the groups to which they were initially randomized: tranexamic acid or placebo. All efficacy analysis will be by an Intent to Treat strategy. Participants will be included in the analysis if they received one or more dose of the study drug, even if participant discontinued participation, cross over between treatment groups or received prophylactic transfusions at a threshold higher than that prescribed in the protocol.

Efficacy analysis on patients will include data gathered on patients from the time of activation of the study drug until discharge or until a point 30 days following activation of the study drug, whichever time point occurs sooner. Any participants who have been consented to participate within the study and randomized to a treatment group but did not meet criteria to begin treatment with the study drug (whether due to development of

exclusion criteria or due to platelet count remaining >30,000/uL) and did not receive any doses of the study drug will not be included in the efficacy analysis.

The population of patients used for analysis of safety will be all patients who receive one or more dose of the study drug. Follow-up for mortality and for thrombotic events will occur at 7 days (+/- 3 days) and 30 days (+/- 3 days) post activation. Adverse events and Serious Adverse events will be based on clinical diagnosis obtained from review of the medical record and by patient report during the surveillance period. Patients will be assessed by daily visits and medical chart reviews by the investigator or study staff during the study period. Patients will be assessed by in-hospital visit (if in patient), clinic visit or telephone (if outpatient) during follow-up period after cessation of the study drug.

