11.5 Statistical Analysis Planned

All statistical comparisons will be based on a two-sided model using a 0.05 level of significance and two-sided 95% confidence intervals.

Data on the number of patients screened, the number of patients eligible for study inclusion, the number of eligible patients who consent to study inclusion and the number of consented patients activated to the study drug will be organized in CONSORT diagram. Run chart may also be used to demonstrate study momentum over time period of study enrollment in graphical form. Suppression of fibrinolysis will be analyzed by matched pair analysis using a T-test of means.

For secondary endpoints, events of WHO Grade 2 or higher bleeding will be compared through the use of odds ratio or T-test statistic of means. The mean number of platelet transfusions will be analyzed using a T-test statistic of means.

Patients will be followed for all clinical outcomes regardless of adherence to the prescribed regimen for the study drug.

Additional statistical analysis will be considered at the time of trial completion based on the data obtained.

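### Aim 4 asks about the number of days with bleeding, but its endpoint records only whether a patient ever bled, and no any-grade analysis is named

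*Combined protocol and SAP*

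**What the plan says.** Section 3.2 states Aim 4 as "To determine whether tranexamic acid leads to a reduction in the number of days with any grade bleeding event". The endpoint printed beneath it is "Proportion of patients with any grade bleeding event following activation of study drug". Section 11.1.2 lists the same quantity among the secondary endpoints: "the proportion of patients with any grade bleeding event following activation of study drug".

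For bleeding, 11.5 names an analysis only at the higher grades: "events of WHO Grade 2 or higher bleeding will be compared through the use of odds ratio or T-test statistic of means". The one other secondary analysis it names is a t-test on platelet transfusions. It closes with "Additional statistical analysis will be considered at the time of trial completion based on the data obtained".

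On the period of observation, 11.3 takes efficacy data "from the time of activation of the study drug until discharge or until a point 30 days following activation of the study drug", whichever comes first. The Synopsis and 8.5 provide for daily bleeding assessment while the patient is on study drug.

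**The concern.** The aim concerns a count per patient, while the endpoint is a yes/no per patient. No section defines a bleeding-day variable, and the proportion appears in two places, so this is not a slip in a single line. Someone following the plan exactly would report a result that does not address the stated aim.

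Two things follow. First, a comparison of bleeding days could enter only through the closing sentence of 11.5, as an analysis chosen after the data are seen. Second, whether a child has ever bled depends on how long the child was watched. Under 11.3 that time ends at discharge or day 30, so it varies between patients. A difference between arms in length of stay could move the proportion with no difference in the daily risk of bleeding.

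**Working it through.** The plan gives no sample size, power or effect size for Aim 4, so there is no figure to reproduce. The check is a comparison of the text, followed by illustrations on assumed inputs.

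**1. Aim against endpoint.**

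| Place | Quantity | Unit |
|---|---|---|
| 3.2, Aim 4 | Days with any-grade bleeding | Count per patient |
| 3.2, Aim 4 endpoint | Any-grade bleed at any time | Yes/no per patient |
| 11.1.2 | Any-grade bleed at any time | Yes/no per patient |
| 11.5 | Nothing for any-grade bleeding | None |

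**2. How far the two quantities can part.** Assume a constant, independent daily bleeding probability p over D days (not a document figure). Expected bleeding days are D × p, and the proportion ever bleeding is 1 − (1 − p)^D.
- p = 0.30, D = 20: days 6.0; ever bled 1 − 0.70^20 = 99.9%. With p halved: days 3.0; ever bled 1 − 0.85^20 = 96.1%.
- p = 0.20, D = 10: days 2.0; ever bled 1 − 0.80^10 = 89.3%. With p halved: days 1.0; ever bled 1 − 0.90^10 = 65.1%.

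Days halve in both cases. The proportion barely moves in the first and falls clearly in the second.

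**3. Dependence on observation time.** Let daily risk differ between children, with mean p = 0.30 and within-patient correlation 0.2 (assumed). The beta parameters are a = 0.30 × 0.8/0.2 = 1.2 and b = 0.70 × 0.8/0.2 = 2.8. The proportion ever bleeding is 1 − Π (2.8 + i)/(4 + i), for i = 0 to D − 1.

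| Days observed | 5 | 10 | 14 | 20 | 30 |
|---|---|---|---|---|---|
| Ever bled | 70% | 83% | 88% | 92% | 95% |

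The daily rate is the same in every column.

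**4. Is a day count more powerful?** Beta-binomial simulation: 10 per arm, 14 days, daily rate halved, two-sided 0.05, t-test on both endpoints, correlation 0.1 to 0.5 (all assumed except the arm size and the level).
- Calibrated to 88% of placebo patients ever bleeding (the Background's upper figure from another cohort, grade not stated): power 20–23% for the proportion and 34–39% for days. Part of that gap comes from the test, whose size is at most 1.4% on the yes/no and about 5% on days.
- Daily 20% to 10%: 14–20% against 12–33%, with no advantage for days from correlation 0.3 upward.

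So there is no general gain.

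**5. What the proposed analysis would give.** With 5 to 30 assessed days and the same 88% calibration, a quasi-Poisson rate ratio with log assessed days as offset (t reference, 18 df) has size 5–6% and power 32–37%. The typical 95% CI is about 0.2 to 1.2 for a true ratio of 0.5. A negative binomial Wald test under similar assumptions had size 8.4%, 6.3% and 4.8% at correlation 0.1, 0.2 and 0.4, with occasional fitting failures. The model should therefore be named exactly.

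**The case against.** The strongest reply is that little depends on this. Any-grade bleeding is not among the key secondary outcomes in the Summary, the Background and 11.7 both disclaim power for bleeding, and a day count can be derived from the daily records. The gap in 11.5 is also not peculiar to Aim 4: no analysis is named for highest grade (Aim 5), red cell transfusions (Aim 6) or time to bleeding (Aim 7). All of this stands, and it limits the weight. It does not make a day comparison prespecified or make the endpoint fit the aim.

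A reader might also infer that the window for any-grade bleeding is in conflict, because 11.1.2 contains "following activation of the study drug and until study drug cessation". The documents do not support that. For bleeding, the phrase attaches to Grade 2 or higher events. The any-grade endpoint has no competing end there, and 11.3 supplies a general efficacy window.

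Nor should one infer that drug cessation is the natural end because daily assessment is scheduled on drug. Section 11.3 calls for intent to treat, and 11.5 for follow-up regardless of adherence. Some stopping reasons in 6.3 are bleeding-related, such as visible hematuria or a prescribed procoagulant. A count ended at cessation could thus be cut short because of bleeding, and an offset does not correct that. In an illustration with a true rate ratio of 0.50 and each bleeding day ending treatment with assumed probability 0.1 to 0.3, the ratio to cessation was about 0.42 to 0.48, tilted towards benefit. The size depends on those assumptions.

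**Conclusion.** The mismatch is certain from the text: Aim 4 asks about days, its endpoint in 3.2 and 11.1.2 does not count them, and 11.5 names no any-grade analysis. As written, the plan does not answer Aim 4. It is worth correcting but does not threaten the trial, whose primary aims are feasibility, safety and suppression of fibrinolysis.

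It would be tempting to add that bleeding days would rescue power. The documents give no daily rates or within-patient correlations to support that, and under some plausible inputs the advantage disappears. At 10 per arm either endpoint is imprecise. The conclusion rests on matching the endpoint to the aim, and needs none of the simulated figures.

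**What to change.** - **3.2 and 11.1.2:** define the Aim 4 endpoint as the number of days with any-grade WHO bleeding per patient. Use days with a completed bleeding assessment as the denominator, over the 11.3 window (activation to discharge or day 30, whichever is sooner).
- **11.5:** name one analysis, a between-arm rate ratio with 95% CI from a quasi-Poisson model with log assessed days as offset. Add a rank test on the per-patient rate as sensitivity analysis. Keep the any-bleed proportion as descriptive. Bleeding days cannot exceed assessed days, so the count model is a practical choice and not the only defensible one.
- **Window:** do not make drug cessation the main end point. Give the on-drug count as a supplementary analysis.
- **8.6 and 11.3:** reconcile these for inpatient days after cessation. Section 8.6 schedules bleeding assessment only at Day 7 and Day 30 after stopping, while 11.3 describes daily visits and chart reviews during the study period. Report assessed days and stopping reasons by arm.

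If only ever having bled was intended, Aim 4 can be reworded and its analysis named instead. That aligns the text but keeps the dependence on observation time.

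The cost is wording and slightly more analysis. On-drug days need no new data collection. Assessed days after cessation may be incomplete unless the reconciled text provides for them, and the interval will be wide at 10 per arm.
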